5.1.2 Exclusion Criteria

- Currently pregnant, breastfeeding³ or expressing gestational desire for the next 2 months.
- Previously received treatment with BZN or NFX (either completely or incompletely);
- Any concomitant use or documented history of using allopurinol or antifungals (ketoconazole, itraconazole and posaconazole);
- History of hypersensitivity, allergic or SAE to any “nitroimidazole”, and/or its components;
- Acute or chronic health problems that, in the informed opinion of the investigator, may interfere with the evaluation of the efficacy and/or safety of the drug. Examples are acute infections, Human Immunodeficiency Virus (HIV) infections, liver disease with liver failure and kidney disease requiring support treatment;
- Signs and/or symptoms of severe cardiac form of CD⁴;
- History of cardiomyopathy, heart failure or severe ventricular arrhythmia of any etiology;
- Alcoholic participants or those with a history of alcohol abuse (considered as intake of >4 drinks on any single day AND >14 drinks per week for men and >3 drinks on any single day AND >7 drinks per week for women);
- Have basic laboratory parameters outside the normal range or parameters that are considered clinically relevant by the physician responsible for the participant;
- Participation in another clinical trial over the past 12 months.

Pregnancy will be considered an exclusion criterion. There is a strong recommendation for not treating pregnant women due to the possibility of teratogenic effects (experiments performed in animal models). There are inconsistent data regarding chronic Chagas disease during pregnancy; some studies showed increased risk of pregnancy loss, prematurity, and neonatal mortality while other studies did not. Since pregnancy data are inconsistent and chronic Chagas disease is generally not life-threatening, use of this

² A subject will be considered fertile if, in the opinion of the researcher, she is biologically capable of having children and is sexually active. Women who are not fertile must meet at least one of the following criteria: have undergone a documented bilateral hysterectomy and/or oophorectomy; Have clinically confirmed ovarian insufficiency; have reached the postmenopausal state, defined as: cessation of regular menstruation for at least 12 consecutive months without alternative pathological or physiological cause. All women of childbearing age should be advised of the risk of teratogenesis and should use barrier contraceptives during the 60-day period of treatment (may additionally maintain other preferred contraceptive methods that are eventually in use).

³ The amount of this drug excreted into milk is much lower than the amount used to treat infants. Therefore, the use of this drug in nursing mothers who receive an indication of treating Chagas disease might be considered acceptable due to low drug levels in breastmilk and safety when given directly to infants. However, in those cases a close follow up of the newborns is recommended to detect and treat any adverse events. For the purpose of the clinical trial, we consider excluding these women since will add a complexity and a responsibility that could not be covered by the study.

⁴ Cardiac involvement will be assessed through clinical interview, physical examination, and electrocardiogram (EKG). Patients with abnormal EKGs (other rhythms than sinus rhythm, right or left bundle branch block, hemiblocks, ventricular extrasystoles, any heart conduction disorders etc.) will undergo an echocardiogram.

drug is not recommended due to risk of embryofetal toxicity.

5.2 Screening Failures

Screening failures are defined as participants who consent to participate in the clinical study but are not subsequently randomly assigned to study treatment. A minimal set of screening failure information is required to ensure transparent reporting of screening failure participants, in order to meet the Consolidated Standards of Reporting Trials publishing requirements and to respond to queries from regulatory authorities. Minimal obligatory information includes demography, screening failure details, eligibility criteria, and any SAE. Individuals who do not meet the criteria for participation in this study (screening failure) can be rescreened if there is a change in their eligibility.

5.3 Recruitment

The clinical trial is embedded in the CUIDA Chagas project. This project includes three separate, but interconnected studies, namely: implementation research, this clinical trial and an RDT algorithm validation study. The implementation study includes a large number of activities, aimed at generating demand among the target population. This will have an effect on the number of new Chagas patients that will be identified and who will feed the pre-existing patient referral circuits.

Due to the nature of the implementation research and the importance of developing and maintaining adequate control actions related to congenital CD, strategies for the recruitment of the study's target population should be widely discussed with health professionals, (health) managers, civil society and patient representation. This discussion will allow for the implementation of feasible and sustainable strategies in different contexts. The different priority populations suitable for the clinical trial will be recruited as follows:

- Women of Childbearing Age: carrying out information and educational campaigns in the community and at the health unit; invitation to women who attend the primary health care units for other reasons (family planning, vaccination, clinical care, prenatal care, etc.); conduct counseling and testing in primary health facilities.
- Household contacts: advising women with *T. cruzi* infection on surveillance of contacts; home visit for active search.

The centers chosen to participate in the study are already considered reference centers for the treatment of Chagas disease and have established track records of high-quality clinical research integrated into clinical care settings. Each center has its own patient referral flows framed within each health system (patients referred from primary care, specialized centers, etc.). This presupposes an added advantage since there are natural patient referral flows (recruitment projections have been made taking into account such data). In this case, doctors who treat the patients will offer them the possibility of participating in the clinical trial as long as they meet all the inclusion criteria and none of the exclusion criteria.

The main steps should take place as follows:

- The Principal Investigator (PI) or his representative will identify among the people seen at the health facility those who meet the inclusion criteria for the study.
- The PI or its representative will obtain further information to confirm the eligibility of individuals (completion of inclusion criteria and absence of exclusion criteria).
- If the individual is eligible, the PI or his designee will obtain his informed consent, as detailed in the SOP "Informed consent process" and in the section 16.

Therefore, considering the baseline recruitment potential of the chosen centers, as well as the context of the entire CUIDA Chagas project, we do not consider necessary the creation of materials specifically designed for the recruitment of patients for the clinical trial.

Sites recruiting patients will be:

- Colombia
 - o Instituto nacional de Salud, Bogotá
 - o Fundación Cardio infantil, Bogotá.
- Bolivia
 - o Hospital Básico de Villa Montes, departamento de Tarija.
 - o Hospital [name] Zurita, de Padilla, departamento de Chuquisaca.

6. Treatments

6.1 Doses and treatment regimens

Subjects will be randomly assigned into one of the following balanced groups:

- **Group A (B300/2)** - BZN (Abarax®, tablet 100mg), 300 mg - 2 weeks: BZN 300 mg, divided in three daily doses, for 2 weeks matching with placebo tablet administered in three daily doses for 6 more weeks.
- **Group B (B300/4)** - BZN (Abarax®, tablet 100mg), 300 mg - 4 weeks: BZN 300 mg, divided in three daily doses, for 4 weeks matching with placebo tablet administered in three daily doses for 4 more weeks.
- **Group C (B300/8)** - BZN (Abarax®, tablet 100mg), BZN 300 mg, divided in three daily doses for 8 weeks.

BZN will be administered as 100mg tablets in blister packaging. Fixed doses of 300 mg will be used during the clinical trial. Participants will be advised that treatment must be taken in three divided doses, accompanied by a meal. During the visits throughout the treatment period, the subject will receive enough medication until the next scheduled visit. Participants are required to bring all remaining study drugs to the end of treatment (EOT) visit in order to check compliance with prescribed treatment and ensure drug accountability. As per recommendations in the BZN package insert, subjects will be advised to abstain from alcohol during treatment.

Placebo tablets will be provided by the same producer of Abarax® and will have the same size, format and include the same excipients as Benznidazol tablets formulation for oral administration. Quality control for both active treatment and placebo will be in charge of the manufacturer, Laboratorio ELEA.

6.2 Rescue treatment

Patients with CD included in this study will be in the chronic phase, and no rescue is envisaged during the treatment period or until the end of the study. All participants in the experimental arm that remain PCR positive at the end of the study will be treated with BZN 5mg/Kg/day, divided in three daily doses for 60 days. In addition, all participants with positive PCR in the standard dose arm will be offered BZN at the cited doses at the end of the study.

6.3 Drugs labelling, packaging

Detailed information on study medication secondary packaging and labelling will be included in the study manual of operations. Minimum information to be included on the study medication label is:

- Name of Sponsor, name and contact details of the PI;
- Study number;
- Name of the drug, dose;
- Pharmaceutical dosage form, route of administration, quantity of dosage units;
- Directions for use;
- “For clinical trial use only”;
- Batch number and treatment number;
- Expiry date and storage conditions.

6.4 Accountability and compliance

BZN/placebo clinical trial kits will be shipped to the referral Clinical Trial Site in each country that will act as the study medication's depot and will distribute the assigned kits to the participating centers during the trial.

Study specific forms will be used for drug accountability. Adequate records on the study medication's receipt, use, return, loss, or other disposition will be documented and maintained by the study site investigators or delegated staff authorized by the study PI. Study monitors will also be in charge of checking for drug accountability during the regular monitoring visits to the study sites. All study treatments must be kept in a locked room at the pharmacy or other designated locations (such as the PI's office) where restricted access by the pharmacist or authorized study personnel and appropriate storage conditions can be ensured.

BZN/placebo clinical trial kits that will be provided for this study will not be used for other purposes other than this protocol. Under no circumstances may the investigator or site staff supply the study treatment

to other investigators or healthcare services or allow the medication to be used in ways other than as directed by this protocol. Participants will be instructed to bring the clinical trial kits during each visit to the study center for review and drug accountability check.

6.5 Storage

BZN does not need to be shipped or stored under refrigeration. However, if local temperatures rise above 30° C, medication should be kept in a room with air conditioning. Site storage conditions and temperature should be monitored by site personnel for adherence to product specifications. Records should be available.

6.6 Treatment assignment

This is a double-blind trial in which neither the participant nor the investigators will know the duration of treatment that has been assigned to each participant. At the moment of the inclusion a consecutive numeric code will be generated. That number will be linked with a randomization code that will correspond to the treatment kit number. That number will never reveal the therapeutic branch designation. Each center will have a randomization list with the inclusion number and the kit number, and a randomization closed envelope which links the kit number with the treatment. To avoid bias in the allocation of treatment groups, randomization will be centralized, and investigators will not have access to the sequence of allocation. Participants will be randomized 1:1:1 to each of the treatment arms and balanced by country.

6.7 Blinding and procedures for unblinding

The process of masking will be done as follows: closed numbered boxes will be made available per participant. Inside, there will be three numbered boxes that will correspond to tablets with an active ingredient 100mg and/or placebo: box 1 for the first two weeks and box 2 for the following two weeks of the treatment and box 3 for the following 4 weeks. All the tablets will be the same, both in shape, color, and taste. Inside each box, cards will be placed where the sequence of the drug intake will be graphically reflected.

Code breaking for any participant should only be done in case of emergencies, eg a threat to the participants life, and may only be done by the investigator or by an authorized person. The Sponsor and trial monitors should be informed promptly of the need for unmasking, ideally before it is done. Notification will be ensured through the use of a specific form, which will include the participant number, the date of opening of the blind, the reason and the signature of both the person responsible for the decision and the PI.

Each center will have randomization envelopes that should only be opened for breaking the codes. Likewise, an SAE form must also be filled out if the reason for breaking the code meets the previously defined criteria.

The possibility that there are situations in which unmasking does not necessarily justify withdrawal of the participant from the trial is contemplated. In such cases, participants should continue with the visits and respective evaluations as planned.

6.8 Concomitant medication

Participants may receive concomitant therapy for medical occurrences during the study. Medications that are considered necessary for the participant's welfare may be prescribed at the discretion of the investigator. However, specific drugs that elevate liver enzymes, are immune-suppressants or are known to have activity against *T. cruzi* should be avoided during the treatment phase of the study. It is requested that women of childbearing age do not initiate contraceptive drugs (pills, injection, implant, or patch) during the 60 days of study drug administration, as these may also be associated with increased liver enzymes (contraception will be avoided with barrier contraceptives). However, contraceptives can be maintained in those women who were already using them prior to the clinical trial. Although it is not a formal exclusion criterion, it is recommended not to take herbal medicines, food supplements and energetic drinks during the treatment period. In case of doubt patients should be advised to ask for permission to its physician. The PI should be contacted in case of any questions regarding concomitant medications.

All concomitant medications taken by the participant during the study, from the date of signature of the informed consent until the last study follow-up visit, will be recorded in the appropriate section of the CRF.

6.9 Adverse reactions to investigational product

In the case of mild or moderate AE, temporary suspension of the administration of BZN will be considered, while severe reactions will lead to an evaluation of permanent treatment suspension.

6.9.1 Hypersensitivity reactions

In the event of a hypersensitivity related AE depending on the severity, the following symptomatic treatment regimen will be followed, at the investigator's discretion:

- Mild AE: cetirizine 10 mg every 24 hours orally (or other similar antihistamine drug).
- Moderate AE: cetirizine 10mg every 12 hours or +/- prednisone 0.5 mg/kg every 24 hours orally.
- Serious AE: cetirizine 10 mg every 8 hours or +/- prednisone 1mg/kg mg every 24 hours orally. Indication of hospitalization will be assessed.

6.9.2 Hepatotoxicity

In the event of hepatotoxicity, a control of liver function (aminotransferase, bilirubin, alkaline phosphatase, gamma glutamate transferase among others), complete blood count (CBC) and narrow coagulation will be carried out (apart from the studies necessary to rule out other possible sources of hepatotoxicity).

If a participant experiences elevation in serum alanine aminotransferase (ALT) and/or aspartate aminotransferase (AST) exceeding three times upper limits of normal (ULN) but less than 8 times ULN, treatment can be continued if the participant is asymptomatic and does not manifest a total bilirubin elevation $>2x$ ULN. If a participant develops signs/symptoms of liver injury (fatigue, nausea, vomiting, right upper quadrant pain/tenderness, dark urine, fever, rash, jaundice, and/or eosinophilia (<5%)), they will be instructed to immediately contact the study site for evaluation. Adequate care will be provided by the investigator, with support from a specialist (hepatologist) as needed. Discontinuation of treatment should be considered if participant presents such symptoms/signs and associated liver transaminase increase $>3x$ ULN. If the values are 5 times above the normal range for liver enzymes, the medication will be discontinued, and the participant's admission will be assessed.

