9.13 Rules for permanently interrupting trial treatment

The Investigator will permanently interrupt the treatment based on the following:

- ALT or AST >5x upper limits of normal (ULN) for more than two weeks;
- ALT or AST >3x ULN and Total bilirubin 2x ULN or International Normalized Ratio (INR) >1.5, known as Hy's law criteria, to be reported as a SAE;
- ALT or AST >3x ULN with the appearance of fatigue, nausea, vomiting, right upper quadrant pain or tenderness, fever, rash, and/or eosinophilia (>5%);
- AE or any other condition which, in the investigator's opinion, would put the participant at undue risk by continuing the trial treatment;
- Major protocol deviation incompatible with the continuation/participation on the trial;
- Any condition that the investigators consider medically necessary to interrupt the treatment, such as:
 - Significant leukopenia (<500 cells/mm³);
 - Severe gastrointestinal symptoms;
 - Severe allergic dermatopathy;
 - Peripheral sensitive neuropathy.
- Pregnancy.

Regardless of the reasons for trial treatment interruption, the investigator will make all necessary arrangements to ensure that the participant receives the appropriate treatment for the relevant medical condition. Rescue treatment will be offered for these participants, if appropriate, upon trial completion.

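### Section 6.9.2 both permits and forbids dosing in asymptomatic participants with ALT/AST from 5x to below 8x ULN, and for symptomatic elevations above 3x ULN it is weaker than section 9.13

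*Protocol*

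**What the plan says.** Two sections of the protocol govern dosing when liver enzymes rise.

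**Section 6.9.2** has three rules in one paragraph:
- Permission, for ALT and/or AST "exceeding three times upper limits of normal (ULN) but less than 8 times ULN, treatment can be continued if the participant is asymptomatic". The participant must also be one who "does not manifest a total bilirubin elevation" above twice ULN.
- Symptoms: "Discontinuation of treatment should be considered if participant presents such symptoms/signs" together with transaminases above 3x ULN. The signs are "fatigue, nausea, vomiting, right upper quadrant pain/tenderness, dark urine, fever, rash, jaundice, and/or eosinophilia (<5" per cent).
- Stop: "If the values are 5 times above the normal range for liver enzymes, the medication will be discontinued", and hospital admission is to be assessed.

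**Section 9.13** opens with "The Investigator will permanently interrupt the treatment based on the following". Two of its bullets matter here:
- "ALT or AST >5x upper limits of normal (ULN) for more than two weeks".
- "ALT or AST >3x ULN with the appearance of fatigue, nausea, vomiting, right upper quadrant pain or tenderness, fever, rash, and/or eosinophilia (>5" per cent).

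A further bullet requires a permanent stop under Hy's law criteria: above 3x ULN with bilirubin at 2x ULN or INR above 1.5.

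Three other sections bear on how these rules are applied. Section 9.8 leaves suspension and permanent stops to the clinician, who is to take the permanent-stop rules into account. Section 9.12 limits the sum of interruptions to 15 days and refers back to 6.9 for resumption. Section 3.2 sends the reader to 6.9 and to a section 8.13 for the discontinuation criteria. Section 8 ends at 8.6, so 9.13 is evidently meant.

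**The concern.** A stopping rule for liver toxicity has to give one answer for a given set of values. Here the permission runs up to 8x ULN while the unconditional stop starts at 5x, so the same participant can fall under both. For symptomatic participants, an investigator who works from the hepatotoxicity section alone finds a discretionary rule, while the section on permanent stops contains a mandatory one.

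What is at stake is participant safety. Two blinded investigators, both reading the protocol carefully, could treat the same result differently. A symptomatic participant above 3x ULN could be kept on drug under 6.9.2 when 9.13 requires a permanent stop.

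**Working it through.** No figure in the plan needs to be reproduced. The check compares the ranges, with x as ALT or AST in multiples of ULN.

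**Asymptomatic, total bilirubin not above 2x ULN**
- Permission (6.9.2): 3 < x < 8, dosing may continue.
- Stop (6.9.2, last sentence): x of 5 or more, drug is discontinued. Read literally, five times above the normal range is 1 + 5 = 6, so x of 6 or more.
- Overlap: 5 ≤ x < 8, or 6 ≤ x < 8 on the literal reading. It is not empty either way.
- Width: the permission spans 8 − 3 = 5 multiples of ULN. The disputed part is 8 − 5 = 3 of these, or 8 − 6 = 2 on the literal reading.
- Test case, x = 6.5: the permission applies (6.5 < 8) and so does the stop (6.5 > 6 > 5).
- Section 9.13: a permanent stop once x > 5 has lasted more than two weeks. This caps continued dosing but does not say whether drug may be given in the meantime.

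**Symptomatic, x > 3**

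| | 6.9.2 | 9.13 |
|---|---|---|
| Force | stopping to be considered | permanent stop mandatory |
| Number of signs | 9 | 7 |
| Dark urine, jaundice | listed | not listed |
| Eosinophilia | below 5% | above 5% |

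- Test case, x = 4 with nausea: 6.9.2 leaves the decision open; 9.13 requires a permanent stop.
- Test case, x = 4 with jaundice: 6.9.2 counts it as a sign. The symptom bullet of 9.13 does not, so a mandatory stop depends on the Hy's law bullet or on another listed sign.

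**Does another section settle it?** Section 9.8 hands the decision to the clinician without ranking the thresholds. Section 9.12 points back to 6.9, where the conflict lies. The cross-reference in 3.2 leads to 6.9 and to a section that does not exist. None of them says which threshold governs.

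**The case against.** **The mandatory sentence overrides the permissive one.** A site that stops at 5x breaches nothing, and a site that obeys 9.13 also satisfies 6.9.2 for symptomatic participants. This stands in part: the mandatory clauses point to the safer action. It does not remove the conflict, because 6.9.2 expressly permits dosing between 5x and 8x, and if the stop always prevails the 8x limit has no function.

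**The 5x sentence was meant for symptomatic participants.** It follows the sentence about symptoms, so this is possible. But it states no such condition, and it would then add little, since 9.13 already requires a permanent stop above 3x ULN with its listed symptoms.

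**Discontinued means paused.** Section 6.9 foresees temporary suspension, and 9.12 allows resumption, so a stop at 5x that becomes permanent after two weeks is a coherent scheme. That would reconcile the 5x sentence with 9.13, but not with the permission to continue.

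**Other safeguards exist.** The Hy's law bullet would often catch jaundice or dark urine, 9.13 has a general undue-risk stop, and the eosinophilia sign and the reference to 8.13 are evident slips. All of this stands. It lowers the practical risk without making the text consistent.

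**Stronger readings that the protocol does not support.** A reader might infer that chemistry goes unchecked between days 14 and 56, so that the two-week rule cannot work. Section 3.2 puts chemistry at every scheduled visit in the 8 weeks, 6.9.2 orders a liver-function control including bilirubin, and the unscheduled adverse event visit includes biochemistry. What remains is a further inconsistency: sections 7, 8.3 and 12 list treatment-period chemistry only at days 14 and 56, and 6.9.2 states no repeat interval. A reader might also count the drug taken during the disputed period as excess exposure. It is dosing within the assigned course and does not measure harm.

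**Conclusion.** The contradiction is real and should be corrected, because it sits in a liver-safety stopping rule. In 6.9.2 it covers asymptomatic participants with bilirubin not above 2x ULN and ALT or AST from 5x (or 6x) to below 8x ULN. Between 6.9.2 and 9.13 it covers every participant above 3x ULN with a symptom on the 9.13 list: one section is discretionary, the other mandatory. The differing symptom lists and the reversed eosinophilia criterion add to this.

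The conclusion rests on the wording alone and needs no assumption about event rates. The protocol gives no frequency for elevations of 5x to 8x ULN, so neither the number of participants affected nor any harm can be quantified.

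Because adverse events leading to discontinuation are the secondary safety endpoint, a reader might infer that the comparison between arms is biased. The protocol does not support that: investigators are blinded to treatment duration, and nothing in the text shows that the ambiguity would favour one arm.

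**What to change.** Amend the wording. The sponsor's safety team should confirm the thresholds.

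1. In 6.9.2, lower the upper limit of the permission from 8x to 5x ULN, and state the stop as a multiple of ULN so that 5x cannot be read as 6x. Restricting the 5x sentence to symptomatic participants would also remove the overlap. It would, however, allow dosing at 5x to 8x until the two-week rule of 9.13 applies, so that choice should be made openly.
2. State that at 5x ULN or above drug is suspended and ALT, AST and total bilirubin are repeated within two weeks. The stop becomes permanent under 9.13 if values above 5x last more than two weeks. Resumption is subject to the 15-day limit of 9.12.
3. Make symptomatic elevation above 3x ULN a permanent stop in 6.9.2, as in 9.13. Use one symptom list in both sections, including dark urine and jaundice, with eosinophilia above 5%.
4. Correct the reference in 3.2 from 8.13 to 9.13, and make 3.2 agree with sections 7, 8.3 and 12 on whether chemistry is taken at week 4.

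The cost is amendment text, site re-training and some repeat tests. Slightly more participants may be stopped at 5x to 8x ULN. No extra participants are needed.
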